SOP	Standard Operating Procedure
SUSAR	Suspected Unexpected Serious Adverse Reaction
t1/2	Apparent terminal half-life
T _{max}	Time to reach peak plasma concentration
ULN	Upper Limit of Normal
US	United States
WBC	White Blood Cell

4 INTRODUCTION AND RATIONALE

4.1 Background Information

Cyclic vomiting syndrome (CVS) is an idiopathic chronic disorder characterized by sudden episodes of nausea and rapid-fire vomiting lasting for 1–5 days followed by symptom-free periods (Hayes et al, 2018). This alternating pattern of disease and disease-free periods distinguishes CVS from other gastrointestinal disorders. There is no current drug therapy approved for treatment of CVS.

CVS is generally described as consisting of four phases. The *inter-episodic phase* occurs between attacks and patients remain relatively asymptomatic. This phase can last for several months. During the *prodromal phase*, some patients describe an 'aura' that lasts for minutes to hours. This phase usually consists of lethargy, anorexia, pallor or abdominal pain or autonomic symptoms such as sweating or salivation. The *hyperemesis phase* usually starts from the early hours of the morning to noon, and is characterized by intense persistent nausea and repeated vomiting. Typically, vomiting peaks in the first hour and then declines lasting at least 24 hours with episodes commonly occurring in the early morning or upon awakening. The vomiting frequency can be up to eight times every hour (Fleisher et al, 2005). This can last for 1–7 days. Finally, the *recovery phase* begins with the cessation of vomiting and ends when energy levels and appetite recover. Antiemetic agents have been reported to be a key component of support care for acute abortive treatment during the prodromal and emetic phases of CVS in adults (Abell et al, 2008). Abortive IV antiemetic agents such as the 5-HT₃ antagonist ondansetron at high doses and granisetron were reported for supportive treatment of acute vomiting episodes in CVS patients (Li and Misiewicz et al, 2003; Yang, 2010; Venkatasubramani, 2007).

Treatment of CVS remains largely based on real-world clinical experience. There is no current drug therapy approved for treatment of CVS. According to guidelines on management of cyclic vomiting syndrome in adults by the American Neurogastroenterology and Motility Society and the Cyclic Vomiting Syndrome Association (Venkatesan et al, 2019), treatment of CVS should be based on a biopsychosocial care model, integrating lifestyle modification, prophylactic and/or abortive medications, and evidenced-based psychotherapy to address psychiatric comorbidity. The guideline recommends using prophylactic medications in moderate-to-severe CVS and offering abortive medications to all patients to terminate an acute attack. For acute attacks, the committee conditionally recommends using serotonin antagonists, such as ondansetron, and/or triptans, such as sumatriptan or aprepitant to abort symptoms. Antiemetic intravenous therapy was reported to be effective for treatment of nausea and vomiting for CVS acute episodes (Jensen, 2015; Moses et al, 2014). Granisetron was reported to be an effective pharmacologic approach used for abortive and supportive care in CVS (Li and Balint, 2000; Li et al, 2008; Li and Misiewicz, 2003).

Granisetron is a highly selective and potent 5-hydroxyltryptamine type 3 (5-HT3) receptor antagonist widely used for over twenty years as an effective antiemetic treatment (Blower, 2003). The efficacy of granisetron in the prevention of nausea and vomiting has been extensively studied in clinical trials and is approved for chemotherapy-induced nausea and vomiting (CINV), radiation-induced nausea and vomiting (RINV), and for postoperative nausea and vomiting (PONV) (Kytril (granisetron hydrochloride) Prescribing Information 2011, Aapro, 2004; Spartinou et al, 2017; Gilmore et al, 2018). Granisetron has also been shown to be effective and well tolerated in special populations, such as patients refractory to antiemetic treatment for gastroparesis (Simmons and Parkman, 2014), bulimia nervosa, cyclic vomiting syndrome, HIV (Evans, 2016) and patients with hepatic or renal impairment with minimal potential for drug-drug interactions (Aapro, 2004).

Antiemetic agents have been reported to be a key component of support care for acute abortive treatment during the prodromal and emetic phases of CVS in adults (Abell et al, 2008). Abortive IV antiemetic agents such as the 5-HT3 antagonist ondansetron at high doses (0.3–0.4 mg/kg up to 24 mg, q. 4–6 hours) and granisetron (10 μ g/kg, q 4–6 hours) were reported for supportive treatment of acute vomiting episodes in CVS patients (Li and Misiewicz et al, 2003; Yang, 2010; Venkatasubramani, 2007). Despite the widespread use of 5-HT3 antagonists in the treatment of CVS, there have been no definitive clinical trials conducted to date.

Alexza Pharmaceuticals (Alexza) is currently developing *Staccato*® Granisetron for Inhalation (*Staccato* Granisetron; AZ-010) as an acute treatment of CVS. *Staccato* Granisetron represents a new dosage form of granisetron. It is a single-use, hand-held, drug-device combination product that delivers aerosolized granisetron. From a drug development perspective, one of the most compelling characteristics of *Staccato* Granisetron is that the drug can be delivered non-invasively with rapid IV-like pharmacokinetics to individuals. In previous clinical studies with *Staccato* Granisetron and a number of drugs using the *Staccato* technology, mean peak plasma concentration was achieved within minutes following inhalation. In a first-in-human, single ascending dose study with *Staccato* Granisetron (AMDC 010-101; refer to CSR: IND 145,487 SN 0009), the median time to maximum plasma concentration was approximately 2 minutes for doses ranging from 0.5–3 mg.

Staccato Granisetron may provide significant benefit for the treatment of CVS since it has rapid pharmacokinetics and bypasses GI absorption of the drug. Because of the simplicity of the delivery, the patient is only required to take a normal breath for delivery of the aerosolized drug. Consequently, inhalation via *Staccato* delivery could provide a non-invasive, rapid delivery of granisetron and lead to a more rapid and effective control of acute vomiting episodes, representing an improvement to existing patient care. Consequently, this study (AMDC 010-201) is designed to assess the effects of *Staccato* Granisetron as an acute treatment during an episode of CVS in patients with moderate to severe disease.

4.2 Study Medication Description

4.2.1 Staccato Granisetron for Inhalation

Staccato granisetron is a hand-held, single dose, single-use drug-device combination product using Alexza's proprietary *Staccato* delivery system. Oral inhalation through the product initiates the controlled rapid heating of a thin film of excipient-free granisetron to form a thermally generated, highly pure drug vapor. The vapor condenses into aerosol particles with a particle size distribution appropriate for efficient delivery to the deep lung. The rapid absorption of the drug provides peak plasma levels in the systemic circulation within minutes after administration.

The principal components of *Staccato* Granisetron (shown schematically below) are as follows:

- Breath sensor: The breath-activation mechanism that initiates actuation of the heat source
- Heat source (i.e., heat package): The mechanism comprised of a reactant coating on the interior surface of a stainless-steel substrate that generates heat to vaporize the drug and produce the aerosol
- Drug coating: The thin film of excipient-free granisetron on the exterior surface of the stainless-steel substrate
- Airway: The medical-grade plastic housing surrounding the heat package; it controls and directs the airflow over the vaporizing drug.

Schematic Side-View of *Staccato* Granisetron

The interior surface of the stainless-steel substrate of the heat package is coated with a mixture of zirconium and molybdenum trioxide powder with a clay binder. When activated, this undergoes a controlled, gasless, oxidation-reduction (redox) reaction that liberates heat. The redox reaction is initiated by a battery-activated starter inserted into the heat package. Inhalation through the product is detected by the breath sensor, causing the starter to initiate the redox reaction and subsequent rapid heating of the substrate to approximately 400°C. Heat then transfers into the film of granisetron that is coated on the exterior surface of the substrate. The granisetron vaporizes in < 1 second, thereby limiting thermal decomposition. The vapor cools in the airflow and condenses to form aerosol particles that are characterized by a mass median aerodynamic diameter in the range of 1.0 to 3.5μ m. The aerosolized granisetron is delivered to the lung within seconds of inhalation through the device.

Each product is packaged inside a sealed foil pouch. Removal of a pull tab from the product renders it ready for use, as indicated by illumination of a green light. Successful dosing is signaled by the extinguishing of the green light.

4.3 Preclinical Information for *Staccato* Granisetron

For a full discussion of the preclinical data generated to date with *Staccato* Granisetron, please see the Investigator Brochure (m1.14.4.1).

4.4 Clinical Information for *Staccato* Granisetron

While granisetron has been available worldwide in various formulations for many years, AZ-010 has been administered to healthy volunteers in a single ascending dose Phase 1 study (AMDC 010-101) and a multiple ascending dose study (AMDC 010-102). Study AMDC 010-101 was designed in 2 parts in separate cohorts of healthy volunteers. The primary objectives for each part are as follows. For Part A the purpose was to examine the tolerability, safety, and pharmacokinetics of single ascending doses of 0.5, 1, and 3 mg of AZ 010 in healthy volunteers. The purpose of Part B was to compare the pharmacokinetics and safety of a single dose of 1 mg of AZ-010 with that of 1 mg granisetron hydrochloride intravenous (IV) injection in healthy volunteers. The study was conducted in a total of 36 subjects at a single clinical research unit. Across the 3 doses of Part A, the drug was generally well tolerated with 3 of 8 subjects (6 AEs in total) in the 0.5 mg cohort, 3 of 8 subjects (6 AEs in total) in the 1 mg cohort, and 0 of 8 subjects in the 3 mg cohort reporting at least 1 adverse events. All adverse events were mild to moderate in severity and there were no serious adverse events (SAE).

Study AMDC 010-102 was designed to examine the tolerability, safety, and pharmacokinetics (PK) of AZ-010 following 7 days of dosing (up to 3 mg) in healthy volunteers. The data obtained from this study were intended to guide selection of safe and tolerable doses for the Phase 2 clinical trial. The study was conducted in a total of 30 subjects (8 for each of the AZ-010 dose groups and 6 for placebo) at a single clinical research unit. Across the 3 doses the drug was generally well tolerated with a total of 13 of 30 subjects (43%) experiencing an AE (7 of 8 subjects for 0.5 mg; 0 of 8 subjects for 1.0 mg; 4 of 8 subjects for 3.0 mg of AZ-010 and 2 of 6 subjects for placebo) There were a total of 30 AEs reported with the most reported for Gastrointestinal disorders (n = 9) and Nervous System disorders (n = 9). There were no clinical laboratory changes for serum chemistry or hematology or any changes in urinalysis between baseline and discharge that were notable. There were no serious adverse events (SAE).

For a full discussion of the clinical data generated to date with *Staccato* granisetron, please see the Investigator Brochure (m1.14.4.1).

5 ETHICS

The procedures set out in this study protocol, pertaining to the conduct, evaluation and documentation of this study, are designed to ensure that the Sponsor and the Investigator abide by Good Clinical Practice (GCP), including but not limited to Title 21 Code of Federal Regulations (CFR) Parts 50, 56, and 312, and the International Council on Harmonization (ICH) guidelines and directives. Compliance with these regulations also constitutes compliance with the ethical principles described in the current revision of the Declaration of Helsinki and applicable local regulatory requirements and law.

The Principal Investigator is responsible for protecting the rights, safety, and welfare of patients under his/her care, and for the control of the medications under investigation. All ethical, regulatory, and legal requirements must be met before the first patient is enrolled in the study.

The Principal Investigator will ensure that all persons assisting with the study are adequately informed about the protocol, any amendments to the protocol, the study drug, and their study-related duties and functions. The Investigator will maintain a list of sub-Investigators and other appropriately qualified persons to whom he or she has delegated significant study-related duties. Individuals ineligible from conducting or working on clinical studies, including those ineligible as a result of debarment under the Generic Drug Enforcement Act of 1992, will not be allowed to conduct or work on studies sponsored by Alexza Pharmaceuticals. The Investigator is required to immediately disclose to Alexza Pharmaceuticals in writing, if any person involved in the conduct of the study is debarred pursuant to a hearing by US FDA under this anti-fraud law, or if any proceeding for debarment is pending, or is (to the best of the Investigator's knowledge) threatened.

5.1 Institutional Review Board (IRB)

The Institutional Review Board (IRB) will meet all FDA requirements governing IRBs according to CFR, Title 21, Part 56. The Investigator (or designee) must submit this study protocol and any amendments, the Sponsor's approved informed consent form(s) (ICF), patient information sheets, patient recruitment materials, and other appropriate documents to the IRB for review and approval. Following review of the submitted materials a copy of the written and dated approval/favorable opinion will be forwarded to the Sponsor (or designee).

Any advertisements used to recruit patients for the study will be reviewed by the Sponsor and the IRB prior to use.

5.2 Written Informed Consent

Prior to performing any study-related activities under this protocol, including screening tests and assessments, written informed consent with the approved ICF must be obtained from the patient. Pre-screening for potential eligibility in person or by telephone may be conducted with an IRB-approved pre-screen script after a patient provides their consent.

The ICF, as specified by the clinical site's IRB, must follow the Protection of Human Subjects regulations listed in the Code of Federal Regulations, Title 21, Part 50. The background of the proposed study, the procedures, the benefits and risks of the study, and that study participation is

voluntary must be explained to the patient. The patient must be given sufficient time to consider whether to participate in the study.

A copy of the ICF, signed and dated by the patient, must be given to the patient. Confirmation of a patient's informed consent must also be documented in the patient's source documentation prior to any testing under this protocol, including screening tests and assessments. The original signed consent form will be retained with the study records.

All ICFs used in this study must be approved by the appropriate IRB and by the Sponsor. The ICF must not be altered without the prior agreement of the relevant IRB and the Sponsor.

6 STUDY OBJECTIVES

6.1 **Primary Objectives**

Objectives:

The primary objectives of the study are to assess:

- The efficacy of AZ-010 as an acute treatment for cyclic vomiting syndrome (CVS) in adult patients.
- The safety of AZ-010 in adult patients with CVS.

7 OVERALL STUDY DESIGN

7.1 Study Design

This is a multicenter, randomized, double-blind, parallel group, placebo-controlled, efficacy and safety study of adult outpatients diagnosed with CVS and experiencing recurring episodes of stereotypical vomiting. Up to 5 administrations of study medication will be allowed in an At Home environment. CVS patients between 18 and 60 years of age who have experienced at least 3 episodes of recurrent vomiting in the last 12 months and 2 episodes in the last 6 months are eligible for participation. Approximately 50 patients will be randomized to each of 3 treatment groups: 1 mg AZ-010, 3 mg AZ-010, or matching *Staccato* Placebo (*Staccato* device without drug coating). Randomization will be stratified by duration of the patient's typical CVS episode into one of the following two categories: 1) Typical episode of CVS lasts 24 hrs or less from the first vomiting/retching event; 2) Typical episode of CVS lasts greater than 24 hrs from the first vomiting/retching event.

There will be 3 Research Clinic visits and a home treatment period:

Patients will be screened at the Research Clinic to determine if they are eligible for study participation no more than 14 days prior to Visit 2. After the study is explained to the patient and the patient has signed an informed consent form (ICF), the investigator will establish the patient's eligibility according to the inclusion and exclusion criteria via the following assessments: Medical history (with particular reference to history of vomiting symptoms, CVS diagnosis, typical duration of CVS episode (hrs vs days), average number of vomiting/retching events in typical CVS episode, frequency of CVS episodes per year, any triggers for CVS episode, other GI conditions that may cause similar symptoms, treatment history, and current medications); full physical examination (including height, weight); vital signs (heart rate, blood pressure while sitting, respiratory rate, temperature); 12-lead electrocardiogram (ECG); blood draw and urine sample for routine clinical labs (chemistry, hematology, urinalysis); and serum pregnancy test (in female participants of child-bearing potential). In light of the COVID-19

pandemic, patients will also be screened for COVID-19 infection and appropriate social distancing and contact procedures should be taken to ensure patient safety when in the clinic.

Patients who continue to be eligible to participate in the study will be asked to return to the Research Clinic for Visit 2. Patients meeting all inclusion criteria and none of the exclusion criteria will be randomized to treatment with either 1 mg AZ-010, 3 mg AZ-010, or placebo in a 1:1:1 ratio (active:active:placebo). Each randomized patient will receive training in the use of the *Staccato* device and detailed instructions for the use of the ePD in the clinic as well as undergo a pre-test self-administration of their randomized study medication. Each patient will be monitored during a 2 hr observation period and have 12-lead ECG (triplicate) assessments at pre-dose and 2, 30, 60, 90, and 120 minutes post dose. If there are no clinically-significant observations or abnormalities on the ECG, including QT prolongation, the patient will be provided with their Patient Kit that contains the remaining 5 unused Staccato devices in addition to the 1 Staccato device that they used in the clinic.

Randomized patients will be asked to treat a subsequent CVS episode (with single daily dosing up to 5 consecutive days) within 12 weeks after the randomization date. Enrolled patients will self-administer the study medication when they know their CVS episode is imminent or as soon as possible after a CVS-related vomiting episode has begun. Patients will interact with their ePD prior to initiation of treatment (if possible) and to capture the study data. The ePD will be used to record the date and time of study medication administration, the number of vomiting and retching events, and the patient reported outcome measures (including the intensity and duration of the CVS episode, severity of abdominal pain, nausea, and anxiety/panic, and characteristics of the nausea, vomiting and retching over defined time periods). In addition, patients will complete a paper questionnaire to record the number of vomiting and retching events within the first 24 hours after dosing. Patients will be instructed to contact the Research Clinic at the earliest possible time after initiation of dosing and at any time should they require rescue medication, medical assistance, or experience an intolerable AE at home during the treatment period. If the number of vomiting and retching events are not recorded on the ePD or the 24 hour vomiting and retching questionnaire and the patient has unused study medication, that patient may be allowed to continue participation in the 12-week Home Treatment Period in order to treat a second CVS episode during this period. Patients will also record in their diary any medications taken during the Home Treatment period. Rescue medications may include any agent(s) from the list described in Section 9.8; however for the purpose of defining the responder endpoint, only anti-emetic medications, benzodiazepines, and triptans will be considered a rescue medication. Patients are encouraged to avoid rescue medication use for the first 2 hrs following treatment with the study medication. The patient will be required to return to the Research Clinic (Visit 3) within 3-5 days from the last study medication administration for final in-clinic assessments, to return the Patient Kit containing the used and unused study medication, ePD, and any other unused supplies. Conversely, patients will be asked to return to the Research Clinic after 12 weeks with their unused Patient Kit if they did not treat a CVS episode within this time period. Visit 3 will include the following assessments: Vital signs; full physical examination; assessment for treatment emergent adverse events; 12-lead ECG, concomitant medications (including rescue medication taken), and clinical labs.

Safety

Patient safety will be monitored throughout the trial by the Investigator and supported by regular review by the Medical Monitor. The subject will be tested to ensure they do not have the Hepatitis B or C virus, HIV, or COVID-19 during the screening period. Chemistry and hematology laboratory values will be assessed prior and subsequent to treatment of the CVS episode. Patients who experience intolerable symptoms during treatment may discontinue the study at the judgement of the Investigator. Patients may withdraw consent at any time.

All safety assessments will be carried out according to the study Schedules of Events (Table 1). Laboratory assessments are listed in the Appendix, Section 17.1 of the protocol. The approximate total blood volume drawn is the trial is shown below.

Sample	# Samples Taken		Sample Volume (Blood Volume		
Hematology	2		4 mL		8mL	
Serology	1	Х	5 mL		5 mL	
Serum Pregnancy	2		5 mL	_	10 mL	
Chemistry	2		8.5 mL		17 mL	
Total					40 mL	

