6.4 ANALYSIS SETS

The following analysis populations are defined.

- Efficacy Population All participants who receive study medication and treated at least 1 episode of vomiting/retching due to their CVS, analyzed according to randomized treatment
- Safety Population All participants who receive study drug
- Per Protocol (PP) Population A PP population (subset of the Efficacy Population) may be decided upon which will exclude participants with important protocol deviations thought to potentially impact conclusions, if a sufficient number of participants with such deviations exist. If so, this population will be defined prior to breaking the blind.

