9 SAFETY

All safety analyses will be conducted on the Safety Population. All safety parameters will be summarized based on the actual treatment group. All safety summaries will be descriptive.

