9.2 CLINICAL LABORATORY EVALUATIONS

Laboratory values will be converted to the project-defined unit of measurement, as applicable, before analysis. Abnormal, clinically significant laboratory values will be reported and summarized as adverse events. Clinical laboratory tests (including recheck values if present) will be listed chronologically. 'H' and 'L', denoting values above or below the reference range (when present), will flag out-of-range results. At each time point, absolute values and change from baseline of the hematology and chemistry variables will be summarized by treatment and time with n, mean, SD, SEM, median, Min, and Max values. The categorical data of the urinalysis will be summarized by treatment and time in frequency tables by variable. Note, in some cases, baseline (the last assessment prior to dosing with randomized treatment) is obtained at the Screening visit.

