Patients will be instructed to contact the Research Clinic at the earliest possible time after initiation of dosing and any time should they require rescue medication, medical assistance or experience an intolerable AE at home during the treatment period. Adverse events will be recorded separately by the patient in a paper diary. In the case of intolerable symptoms following study medication administration, the patient may take a rescue medication. Permitted rescue medications will not be provided to the patient, but it may include any agent(s) defined in the list in Section 9.8. Patients will record in their paper diary any medications taken during the Home Treatment period. Patients are encouraged to avoid rescue medication use for the first 2 hrs following treatment with the study medication. In the case of extreme distress, the patient should contact the clinical site and/or receive treatment from a health care facility.

Patients will be instructed to contact the study site when a CVS episode and dosing occurs (and study sites should try to contact a patient when they receive a notification that that patient has dosed) so that the study site may schedule the Follow up Visit to the clinic within 3–5 days after the last dose of study medication is taken (or if the 12-week treatment period has expired and the patient has not yet treated a CVS episode). These latter patients will be excluded from the efficacy analyses since they did not take any study medication to treat a CVS episode.

If the number of vomiting and retching events are not recorded on the ePD or the 24 hour vomiting and retching questionnaire and the patient has unused study medication, that patient may be allowed to continue participation in the 12-week Home Treatment Period in order to treat a second CVS episode during this period.

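### The Visit 3 laboratory row pools participants seen 3-5 days after home dosing with clinic-dose-only participants seen about 12 weeks later, which would dilute any laboratory effect lasting days but not weeks

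*Combined protocol and SAP*

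**What the plan says.** Protocol 7.1 (Safety) describes the laboratory work in relation to the treated episode: "Chemistry and hematology laboratory values will be assessed prior and subsequent to treatment of the CVS episode". Table 1 schedules clinical laboratory testing only at Visit 1 and Visit 3, so Visit 3 is the only draw after dosing.

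At Visit 2 all randomized participants "undergo a pre-test self-administration of their randomized study medication" (protocol 7.1). SAP 6.4 defines the "Safety Population All participants who receive study drug", so the clinic dose alone is enough for membership.

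Visit 3 has two timings. Those who dose at home return "within 3-5 days from the last study medication administration". Those who treat no episode are covered by a different rule: "patients will be asked to return to the Research Clinic after 12 weeks with their unused Patient Kit". Protocol 7.6.3 schedules the same Follow-up Visit for this second group ("or if the 12-week treatment period has expired and the patient has not yet treated a CVS episode"), and protocol 7.6.4 has routine laboratory samples taken from everyone who completes. Protocol 8.3.1 adds a third possible timing, because those who stop early have the Visit 3 assessments at early termination.

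On analysis, SAP 9 states: "All safety analyses will be conducted on the Safety Population". SAP 9.2 adds: "At each time point, absolute values and change from baseline of the hematology and chemistry variables will be summarized by treatment and time". Urinalysis categories are tabulated in the same way. Neither section splits by home dosing or by time since last dose, and SAP 6.8 plans no subgroups.

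**The concern.** The comparison that protocol 7.1 describes, laboratory values before and after a treated episode, is not what the SAP table would show. For a participant who never doses at home there is no treated episode, and the Visit 3 sample is taken about 12 weeks after a single dose. For a home-dosed participant it follows two to six doses in all (one in clinic plus one to five at home), the last of them 3-5 days earlier. Averaging the two gives a mean change that describes neither exposure.

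The plan recognizes the difference for efficacy: SAP 6.1 and protocol 7.6.3 remove participants who did not treat an episode. There is no matching rule for the laboratory tables. Safety is one of the two primary objectives. What is at stake is how well the only post-dose laboratory summary can show a modest shift in means or in urinalysis frequencies.

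**Working it through.** **Check on the number of draws.** The blood-volume table in protocol 7.1 gives two hematology, one serology, two pregnancy and two chemistry samples: 2 x 4 + 1 x 5 + 2 x 5 + 2 x 8.5 = 40 mL, which reproduces the stated total. Two chemistry and two hematology samples agree with Table 1: one before dosing and one at Visit 3.

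**Time since last dose.** Protocol 7.4 gives a half-life of 10 hr.
- Home-dosed: 3-5 days = 72-120 hr, so 72/10 = 7.2 to 120/10 = 12 half-lives.
- Clinic dose only: 12 weeks = 12 x 7 x 24 = 2016 hr, so about 202 half-lives.

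At 7.2 to 12 half-lives the fraction of a dose remaining is 2^-7.2 = 0.7% to 2^-12 = 0.02%. Both groups are therefore sampled essentially off drug. Dilution can affect only a laboratory effect that outlasts the drug by days and is gone by 12 weeks.

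**Dilution.** Let f be the share of an arm's participants with Visit 3 laboratory data who had no home dose. Let delta be the mean shift in the home-dosed, and take the residual shift in the others as 0.

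Pooled mean shift = (1 - f) x delta + f x 0 = (1 - f) x delta.

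The same factor applies to the active-minus-placebo difference if f is similar across arms, so reading against placebo does not undo the dilution. It also applies to an excess frequency of abnormal urinalysis results.

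**Value of f.** The documents do not give it. As an illustration, assume that episodes follow a Poisson process and that every episode is treated. Then f = exp(-rate x 12 weeks). Inclusion criterion 3 requires at least 3 episodes in the prior year and 2 in the past 6 months. The higher rates below are assumptions.

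| Assumed rate | f | Share of shift kept | A 10-unit shift appears as | Home-dosed per arm of 50 |
|---|---|---|---|---|
| 3 per year | exp(-12 x 3/52) = 0.50 | 0.50 | 5.0 | 25 |
| 2 per 6 months | exp(-12 x 2/26) = 0.40 | 0.60 | 6.0 | 30 |
| 3 per 6 months | exp(-12 x 3/26) = 0.25 | 0.75 | 7.5 | 37-38 |
| 4 per 6 months | exp(-12 x 4/26) = 0.16 | 0.84 | 8.4 | 42 |
| 6 per 6 months | exp(-12 x 6/26) = 0.06 | 0.94 | 9.4 | 47 |

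The last column takes 50 per arm from SAP 6.2 and assumes that all 50 have Visit 3 laboratory data. The first two rows put every participant at the eligibility floor, so they lie near the upper end of f under this assumption.

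**The case against.** The strongest reply is that summarizing safety on everyone dosed is conventional and that little is hidden here. SAP 9 makes all safety summaries descriptive, so no test loses validity or power. SAP 9.2 reports clinically significant values as adverse events, lists every result with high and low flags, and tabulates minimum and maximum, which pooling does not average down. SAP 8.6 lists dosing by participant, so a determined reader could separate the groups. All of this stands, and it is why the point is small. It does not recover a modest shift in means or frequencies, which listings show poorly.

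A reader might infer more than the documents support in four ways:
- **That a real drug effect is being understated in the active arms.** No such effect is established. Protocol 4.4 reports no notable change in chemistry, hematology or urinalysis after 7 days of dosing up to 3 mg. That was a study of 30 healthy volunteers and not proof of absence, but the shift remains hypothetical.
- **That the contrast is exposed against unexposed.** With a 10 hr half-life, both groups are sampled off drug.
- **That 40-50% will never dose at home.** That requires every participant to be at the entry minimum, and the documents state no expected share.
- **That the ECG tables share the problem.** Protocol 7.6.2 takes triplicate ECGs from 2 to 120 minutes after the clinic dose in every dosed participant, so the readings that matter most for drug effect do not depend on Visit 3.

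SAP 8 does mention summaries for both the Safety and Efficacy populations. That sentence concerns participant information and yields to statements elsewhere, and SAP 9 places all safety analyses on the Safety Population.

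**Conclusion.** The pooling follows directly from the current text, and the resulting row does not give the comparison around a treated episode that protocol 7.1 describes. Its effect is conditional. If a laboratory effect lasts for days but not for 12 weeks, the pooled Visit 3 mean shift is (1 - f) of the shift in home-dosed participants. Under the Poisson illustration that is 50-60% at the entry minimum and 75%, 84% and 94% at 3, 4 and 6 episodes per 6 months. The direction needs only f above zero and no residual effect at 12 weeks. The size rests on an assumed rate. Because the summaries are descriptive and individual abnormalities remain visible, this is a minor improvement to a table, not a defect that endangers a conclusion.

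**What to change.** In SAP 9.2, keep the pooled Safety Population row and add two presentations of Visit 3 change from baseline and urinalysis frequencies, by actual treatment:
- Participants with at least one home dose. Read the active arms against placebo, because change within an arm also reflects the recent vomiting episode and any rescue medication.
- Participants with the clinic dose only, shown separately with days since last dose, so that early terminations can be told apart from 12-week returns.

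The cost is one grouping variable and one derived interval. SAP 8.1 already counts participants treated in the home phase, so the flag is needed anyway. No new data and no change in conduct are required, and SAP 3 already provides for justifying changed analyses in the study report.

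The limitation should be stated with the tables. The split is on a post-randomization event, the groups are smaller (25 to 47 home-dosed per arm of 50 in the illustration), and a single home dose qualifies, so the home-dosed row is not purely a repeat-dose group. It is descriptive only.
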